15.8 Occult Malignancy

Occult Malignancy will be determined by occult blood in stools (hemocult test), finding on chest x-ray, carcinoembryonic antigen, prostate-specific antigen (males only), cancer antigen 125 (females only), α -fetoprotein, and β -hCG.

15.9 CESD-R

The Center for Epidemiologic Studies Depression Scale Revised will be used for screening for depression and depressive disorder.

15.10 Clinical Stroke Evaluations

Detailed information regarding clinical stroke evaluations (including sample forms and instructions for conducting the evaluations) will be provided separately from this protocol.

Fugl-Meyer Motor Score (FMMS)

FMMS will be calculated as change from baseline for Months 1, 3, 6 (primary), 9 and 12. The treatment group will be compared to the control group based on the relative proportion of subjects who improve at least 10 points.

Modified Rankin Scale (mRS)

The mRS will be calculated to determine eligibility (mRS 2-4) at screening and again at Baseline, Months 1, 3, 6 (secondary), 9 and 12 months. The treatment group will be compared to the control group based on based on the relative proportion of subjects who improve at least

1 point. The mRS for all assessments except the Screening assessment will be recorded on video and reviewed in a blinded fashion by a central external rater.

Motricity Index

To ensure subjects have a defined motor deficit, an assessment of the subject's Motricity Index will be calculated at Screening for study eligibility purposes. Subjects will require either Motricity Index 30-75 (Upper Extremity Scale) OR 27-74 (Lower Extremity Scale).

Action Research Arm Test (ARAT)

ARAT scores will be calculated at Baseline and Months 1, 3, 6 (secondary), 9 and 12. The treatment group will be compared to the control group based on the relative proportion of subjects who improve at least 6 points.

Gait Velocity

Gait Velocity on a standard 10 m walk will be calculated at Baseline and Months 1, 3, 6 (secondary), 9 and 12. The treatment group will be compared to the control group based on the relative proportion of subjects who improve at least one functional level (e.g. from <0.4 m/s to 0.4-0.8 m/s or from 0.4-0.8 m/s to >0.8 m/s).

NeuroQOL

Two subdomains of the NeuroQOL will be assessed at Baseline and Months 1, 3, 6 (secondary), 9 and 12 using the Short Forms. The 2 subdomains include: Upper Extremity Function (Fine motor ADL) and Lower Extremity Function (Mobility). The treatment group will be compared to the control group based on the mean change in T Scores from baseline.

Global Rating of Perceived change from Baseline

This assessment will be performed at Months 1, 3, 6 (secondary), 9 and 12. It will be performed by both subject (may be completed by caregiver) and clinician. Subjects and clinicians will be asked about perceived changes in their motor function by comparing "how well they are doing compared to before the surgical procedure". The subject global rating of perceived change should be completed by the subject. In the event the subject is not able to complete the questionnaire, the caregiver will be allowed to ask the questions of the subject and complete the questionnaire using the subject's answer(s). The following 7-point Likert scale will be used:

- Score 7 = Much better
- Score 6 = A little better, meaningful
- Score 5 = A little better, not meaningful
- Score 4 = About the same
- Score 3 = A little worse, not meaningful
- Score 2 = A little worse, meaningful

- Score 1 = Much worse

15.11 Physiotherapy

Subjects will be instructed on of a set of exercises (cylinder grasp, thumb raise, stand and squat, walk) to be carried out at home every morning and afternoon while in the study. Subjects will be asked to keep a daily diary of their performance of the exercises.

Physical therapy treatment during the study will be recorded in the CRF.

15.12 Leg Activity Monitoring

Bilateral ankle sensors will be worn by subjects for 2 week intervals at Screening (Day -14), Baseline (Day -1) and Months 1, 3, 6, and 9. Data will be provided to a centralized reviewer for analysis. Detailed information regarding leg activity monitoring will be provided separately from this protocol.

15.13 Imaging (MRI), Chest X-Ray, CT, and ECG

MRI

Magnetic Resonance Imaging (MRI) of the brain will be obtained using either a 1.5 or 3 Tesla MRI scanner. Each subject should have all scans conducted on the same scanner if possible (excepting those used for stereotactic planning and post-operative assessments, within 2 weeks of the surgery (implant/sham). Standard T1 and T2 sequences and FLAIR will be obtained, and will be recorded in standard digital format for review. Contrast is to be utilized for MRI procedures at Baseline (Visit 2), Day of surgery (Visit 3B), Day 8 (Visit 5), Month 1 (Visit 6), and Month 12 (Visit 10); all other scheduled MRI to be performed without contrast.

Diffusion tensor imaging (DTI) is an MRI technique which characterizes the magnitude, anisotropy and orientation of the diffusion tensor, using the pulsed-gradient, spin echo pulse sequence with a single-shot, echo planar imaging readout. DTI data will be obtained using whole brain coverage, a maximum of 2.5 mm isotropic resolution and at least 30 diffusion encoding directions and may be obtained using either a 1.5 or 3 Tesla MRI scanner. DTI is required for subjects at assessment sites with DTI capability. DTI is optional for sites without access to DTI-compatible scanners. Perfusion imaging, including DSC, is also required for subjects at assessment sites when the MRI has the capacity.

A centralized imaging core laboratory will be used to confirm lesion size for analysis purposes, develop imaging acquisition protocols, and conduct imaging processing and analyses.

Detailed information regarding MRI procedures will be provided separately from this protocol.

Chest X-ray

Standard chest x-ray techniques will be performed according to the schedule described above.

CT Scans

Standard CT techniques will be performed according to the schedule described above. CT is to be conducted without contrast.

Electrocardiograms

All ECGs will be obtained in the supine position, after the subject has been resting supine for at least 10 minutes. ECGs will be 12 lead with a 10 second rhythm strip. ECGs should be obtained prior to drawing blood samples. With the exception of Visit 3 ECG, all attempts should be made to use the same ECG recorder for all visits within individual subjects. ECGs will be centrally read at a core lab according to established quality assurance procedures for inter/intra reader variability. ECGs will be reviewed, signed and dated by the Investigator listed on the Form FDA 1572 (MD or DO) after each ECG collection. The same Investigator should review all ECG reports for a given subject whenever possible.

16.0 ADVERSE EVENTS

16.1 General Information

An **adverse event** (AE) is any untoward medical occurrence in a patient or clinical investigation subject enrolled in the study and that does not necessarily have a causal relationship with this treatment. An AE can therefore be any unfavorable and unintended sign, symptom, or disease temporally associated with the use of an investigational product, whether or not considered related to the investigational product. This includes any side effects, injury, toxicity, or sensitivity reaction, and may include a single symptom or sign, a set of related symptoms or signs, or a disease. An adverse event is also any laboratory abnormality judged to be clinically significant by the Investigator or Sub-investigator(s) that worsened compared to Baseline.

Throughout the course of the study, every effort should be made to remain alert to possible adverse experiences. Patients should be encouraged to report adverse events spontaneously or in response to general, non-directed questioning.

With the occurrence of an adverse event, the primary concern is the safety of the patient. If necessary, appropriate medical intervention should be provided.

An AE **does not** include:

- Medical or surgical procedures (*e.g.*, surgery, endoscopy, tooth extraction, transfusion); the condition that leads to the procedure is an adverse event
- Pre-existing diseases or conditions present or detected at the start of the study that do not worsen in severity or frequency
- Situations where an untoward medical occurrence has not occurred (*e.g.*, hospitalization for elective surgery, social and/or convenience admissions)
- Overdose of concomitant medication without any signs or symptoms

A **Serious Adverse Event (SAE)** is any adverse event that results in any of the following:

- death,
- life-threatening event,
- hospitalization or prolongation of hospitalization,
- a persistent or significant disability/incapacity,
- congenital anomaly/birth defect, or
- an event that may require intervention to prevent any one of the other outcomes listed above (based on medical judgment)

An Unexpected Adverse Event is any AE that is not identified in nature, severity, or frequency in the current Investigator's Brochure or product information. Adverse events assessed as related to surgical procedure, and Clavien-Dindo Classification (<http://www.surgicalcomplication.info/index-2.html>) Grade II or higher would be considered unexpected or unanticipated, unless such event has been previously reported and documented in the IB.

A Serious and Unexpected Suspected Adverse Reaction (SUSAR) is an adverse reaction to study product or surgical procedure that is both serious and unexpected and for which there is a reasonable possibility that the study product or surgical procedure caused the adverse event.

All SUSARs will be submitted as expedited reports to the FDA. For this study, serious and unexpected AEs involving neurological deterioration, procedural complications, seizures, benign and malignant tumors and pregnancy will also be submitted as expedited reports, regardless of attribution.

16.2 Adverse Event Reporting Period

The adverse event reporting period for this trial begins upon informed consent and ends 12 months after the administration of SB623, or at Early Termination.

All AEs (both serious and non-serious) should be followed until resolution or until a stable clinical endpoint is reached. All measures required for AE management and the ultimate outcome of the AE must be recorded in the source document.

16.3 Recording of AEs

All AEs, regardless of severity, seriousness, or presumed relationship to Study Product, must be recorded using medical terminology in the source document and on the CRF. Events will be recorded at all study sites using standard terminology provided by the Sponsor or designate (*e.g.*, CRO), such as MedDRA terminology.

The WHO (World Health Organization) Standard Toxicity Criteria (STC) will be used to assist in categorizing and grading adverse events. A copy of the WHO STC will be provided in the study documents. Whenever possible, a diagnosis should be given when signs and symptoms are due to common etiology (*e.g.*, cough, runny nose, sneezing, sore throat, and head congestion should be reported as “upper respiratory infection”).

16.4 Assessing Relationship of AE to Study Product

The Investigator must record his/her opinion concerning the relationship of the AE to study therapy on the Adverse Event CRF. Table 4 below provides guidance for assigning relationship to Study Product.

Table 4: Relationship of Adverse Event to the Administration of the Study Product or Surgery

Not related	No temporal relationship to cell treatment/procedure, or the presence of a reasonable causal relationship between another drug, concurrent disease, or circumstance and the adverse event (AE).
Unlikely related	A temporal relationship to cell treatment/procedure, but no reasonable causal relationship between cell treatment/procedure and the AE.
Possibly related	A reasonable causal relationship between the cell treatment/procedure and the AE. Information related to withdrawal of cell treatment/procedure was lacking or unclear.
Probably related	A reasonable causal relationship between the cell treatment/procedure and the AE. The event responded to withdrawal of cell treatment/procedure.
Definitely related	A reasonable causal relationship between the cell treatment/procedure and the AE. The event responded to withdrawal of the cell treatment/procedure.

16.5 Reporting Serious Adverse Events

Any Serious Adverse Event, including death that occurs during this study, whether or not the event is considered to be related to the study product or surgical procedure, must be reported immediately (**within 24 hours after the site becomes aware of the event**) to the Safety Monitor (ProPharma Group/PROSAR).

The contact information for reporting SAEs is as follows:

Safety Monitor: [name], BSN (ProPharma Group/PROSAR)

Email: [contact]

[contact]

The Investigator is encouraged to discuss with the Unblinded Medical Monitor any adverse experiences for which the issue of reportability is unclear or questioned.

A verbal SAE notification must be followed by a completed Serious Adverse Event Report form signed by the Investigator within 24 hours. The report should be as complete as possible without delaying ProPharma Group/PROSAR notification.

Any SAE follow-up information requested by ProPharma Group/PROSAR should be provided in a timely manner.

Upon receipt of notification of any Serious Adverse Event, ProPharma Group/PROSAR, the Unblinded Medical Monitor and the Sponsor will immediately conduct an evaluation of the event and take action indicated by the results of the evaluation. This may include notification to applicable regulatory authorities/federal agencies, other Investigators, IRBs and/or the suspension or termination of the study. The Sponsor will remain blinded during this process. The Investigator is required to report all IND Safety Reports to the local Ethics Committee (EC) or Institutional Review Board (IRB)/Institutional Biosafety Committee (IBC) in accordance with the EC/IRB bylaws.

All additional follow-up evaluations of the SAE must be reported to ProPharma Group/PROSAR. These data should be sent by email as scanned copy or faxed to the Safety Monitor at [contact] as soon as they are available.

16.6 Follow-up of Adverse Events

All AEs (both serious and non-serious) should be followed until resolution or until a stable clinical endpoint is reached. All measures required for AE management and the ultimate outcome of the AE must be recorded in the source document.

17.0 EXTERNAL DATA SAFETY MONITORING BOARD

An External Data Safety Monitoring Board (DSMB) will evaluate safety and toxicity and mortality rates, and recommend appropriate actions, according to the DSMB Charter. The DSMB will review ongoing study data within one month of the enrollment of subjects at the 25%, 50%, and 75% of the total population. In addition, two or more serious adverse events potentially attributed to SB623 as assessed by the Investigator will trigger a review by the DSMB before continuing enrollment.

18.0 STATISTICAL METHODS

18.1 Analysis Populations

18.1.1 Efficacy Population

The intent-to-treat (ITT) population will include all randomized patients. All efficacy analyses will utilize this population.

18.1.2 Safety Population

The safety population will include all randomized patients that undergo surgery. All safety analyses will utilize this population.

18.2 Statistical Analysis

The Statistical Analysis Plan (SAP) will provide details on the statistical methods planned for this study, and it will be finalized prior to the clinical study database is locked and the treatment is unblinded.

In general, demographics and baseline characteristics will be presented by treatment group. Continuous variables will be summarized by the following descriptive statistics: sample size, mean, median, standard deviation, minimum, and maximum. Discrete variables will be summarized by frequencies and percentages (contingency tables).

18.2.1 Analysis of Efficacy

All efficacy analyses will be performed on the modified intention to treat (mITT) population, which is defined as all randomized patients who complete the surgery treatment procedure (or sham).

18.2.1.1 Primary Efficacy Analysis

The primary analysis will be a comparison of the proportion of SB623 treated subjects (pooling both SB623 doses) to sham surgical controls that achieve an improvement of at least 10 points on the Fugl-Meyer Motor Scale at 6 months from Baseline. A generalized linear mixed model (GLMM) will be utilized using the mITT population. The GLMM model will have the outcome variable, responder of FMMS (either \geq or <10 points improvement in FMMS at Month 6), and independent variables of treatment (SB623 combined doses vs. sham surgical control), FMMS baseline score and pooled surgical site as fixed effects.

Hypothesis

Let $P_{\text{SB623_combined doses}}$ and P_{Placebo} represent the proportions of responders who have an improvement of at least 10 points on the Fugl-Meyer Motor Scale at 6 months from Baseline in SB623 combined doses and placebo, respectively. The primary analysis will test the following hypothesis

$$H_0: P_{\text{SB623_combined doses}} = P_{\text{Placebo}} \text{ versus the alternate } H_1: P_{\text{SB623_combined doses}} \neq P_{\text{Placebo}}$$

18.2.1.2 Secondary Efficacy Analyses

Secondary analyses will evaluate a number of endpoints:

- The proportion of SB623 treated subjects (pooling both SB623 doses) that improve at least 1 point on the Modified Rankin Scale (mRS) will be analyzed at 6 months (from

Baseline) using a similar GLMM model to the primary efficacy analysis. The GLMM model will include treatment (SB623 combined doses vs. sham surgical control), mRS baseline score and pooled surgical site as fixed effects.

- The proportion of SB623 treated subjects (pooling both SB623 doses) that improve at least 6 points on the Action Research Arm Test will be compared to sham-surgery controls at 6 months (from Baseline) using a similar GLMM model to the primary efficacy analysis. The GLMM model will include treatment (SB623 combined doses vs. sham surgical control), ARAT baseline score and pooled surgical site as fixed effects.
- The proportion of SB623 treated subjects (pooling both SB623 doses) that improve at least 1 functional level on Gait Velocity will be compared to sham-surgery controls at 6 months (from Baseline) using a similar GLMM model to the primary efficacy analysis. The GLMM model will include treatment (SB623 combined doses vs. sham surgical control), Gait Velocity baseline score and pooled surgical site as fixed effects.
- The mean change in the two of the four NeuroQOL subdomain T scores of SB623 treated subjects (pooling both SB623 doses) will be compared to sham-surgery controls at 6 months (from Baseline) using a mixed model repeated measures model (MMRM). The two subdomains include:
 - Upper Extremity Function (Fine Motor ADL)
 - Lower Extremity Function (Mobility)

The MMRM model will include treatment, visit, pooled site, corresponding baseline subdomain T score, and the treatment-by-visit interactions. Restricted Maximum Likelihood Estimation procedure will be employed using an unstructured covariance matrix. Missing observations will not be imputed for this analysis.

- The proportion of SB623 treated subjects (pooling both SB623 doses) scoring either 7 (much better) or 6 (a little better, meaningful) on the Global Rating of Perceived Change by both Subject and Clinician will be compared to sham-surgery controls at 6 months (from Baseline) using a logistic regression model with treatment (SB623 vs. sham placebo) and pooled center as the covariates. The outcome variable of this analysis is a dichotomized variable based on of the Global Rating of Perceived Change score (≥ 6 vs. < 6).
- All efficacy endpoints mentioned above will be analyzed to assess the treatment difference between SB623 2.5-million and 5-million cells groups. The same statistical methodologies to evaluate SB623 combined doses vs. surgical sham control for each efficacy endpoint will be used.

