7. GENERAL ASPECTS FOR STATISTICAL ANALYSIS

7.1. GENERAL METHODS

Statistical methodology and analyses are in accordance with the principles outlined by the International Conference on Harmonization (ICH) E9 guidelines. All statistical analyses will be done using SAS statistical software version 9.3 or higher.

- All summary tables will be presented by treatment group and displayed as 2.5 million SB623 cells, 5 million SB623 cells, Combined SB623 cells, and Sham Surgery for the efficacy analyses. A total column will be presented, wherever necessary.
- Continuous variables will be summarized using descriptive statistics which will include the following: the number of observations (n), mean, standard deviation (SD), median, minimum (Min), and maximum (Max).
- Categorical variables will be summarized using number of observations (n), frequency and percentages of subjects. All percentages will be based on the number of subjects without missing data, unless otherwise specified.
- All statistical testing on treatment effects will be conducted at a 2-sided alpha level of 0.05 and confidence intervals (CI) will be calculated at 95% for SB623 2.5 million and 5 million, separated and combined treatment group versus Sham control, unless otherwise stated.
- All relevant data collected in the database will be included in data listings and sorted by treatment group, subject number, test/measurement, and visit and time point as appropriate. The treatment group will be displayed in the same order as shown in the summary tables.
- Measurements from subjects excluded from the pre-defined analysis populations or extra measurements (such as unscheduled or repeat assessments) will not be included in summary tables unless otherwise specified. Unscheduled and early termination data will be included for definition of LOCF Endpoint or overall assessments. Data listings will present all data, including unscheduled, repeated and early termination data, regardless of visit.

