9. EFFICACY

Descriptive summary statistics will be presented for actual measurement values and for changes from baseline by visit for the continuous variables. Number and percent of subjects will be summarized for each visit for the categorical variables.

Generalized Linear Mixed Model (GLMM) will be used for analysis of the primary endpoint FMMS response rate and the secondary endpoints mRS/ARAT/Gait Velocity/global ratings of perceived change response rate. Adjusted odds ratios and 95% confidence intervals (CIs) will be reported for the comparison of combined SB623 group versus sham control and separately for the comparisons of each SB623 group versus sham control.

Mixed Model for Repeated Measures (MMRM) analysis will be used to analyze continuous variables with more than one post-baseline assessment, whereas Analysis of Covariance (ANCOVA) will be used for continuous variables with one post-baseline assessment.

All efficacy analysis will be performed on the mITT population. The primary (FMMS response) and the key secondary endpoint (mRS) will be performed on the per protocol population as well. Details are given in Sections 9.1 and 9.2 below.

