A GLMM model will be utilized using the mITT population as primary analysis. The GLMM model will have the outcome variable, FMMS responder (either \geq or $<$ 10 points improvement in FMMS), and independent variables of treatment, visit, treatment and visit interaction, and pooled surgical site as effects, and baseline FMMS motor total score and baseline mRS score as covariates. Treatment, visit, and pooled surgical site will be treated as categorical variables. Visit will be fitted as a repeated effect within subject. Link function will be set to logit and distribution to binary. An unstructured variance-covariance structure will be used. If this fails to converge then the following variance-covariance structures will be used based on the step-down order until model convergence is obtained: heterogeneous Toeplitz, heterogeneous autoregressive, heterogeneous compound symmetry, and then compound symmetry. The Kenward-Roger method will be used to estimate the denominator degrees of freedom. Adjusted odds ratios and 95% CIs for each visit will be presented for combined SB623 versus sham control. A separate analysis will be repeated for the comparisons of each SB623 group versus sham control for FMMS response. A forest plot of odds ratios and 95% CIs will be presented for individual/combined SB623 versus sham control. The results for Month 6 will be the primary interest.

For FMMS response, a supportive analysis will also be conducted based on the per protocol population using the same statistical method and following the same process for selection of variance-covariance structure.

A logistic regression analysis will be conducted by visit to include FMMS response as outcome variable, and independent variables of treatment and pooled surgical site as effects, and baseline FMMS motor total score and baseline mRS score as covariates. Odds ratios and 95% CIs will be reported for each visit.

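### The protocol calls for a direct 2.5-million versus 5-million comparison on every primary and secondary efficacy endpoint; the SAP plans only comparisons with sham and does not explain the gap

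*Protocol*

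**What the plan says.** **Protocol.** Section 18.2.1.2 lists the secondary analyses and ends with a requirement on dose: every efficacy endpoint named up to that point is to be "analyzed to assess the treatment difference between SB623 2.5-million and 5-million cells groups". It also fixes the method: "The same statistical methodologies to evaluate SB623 combined doses vs. surgical sham control for each efficacy endpoint will be used". The endpoints concerned are FMMS response (primary, section 18.2.1.1), mRS, ARAT and gait velocity response, the two NeuroQOL T scores and the Global Rating of Perceived Change.

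**SAP.** The general rule in section 7.1 sets tests and intervals for "SB623 2.5 million and 5 million, separated and combined treatment group versus Sham control, unless otherwise stated". Section 9 plans adjusted odds ratios for the "comparison of combined SB623 group versus sham control and separately for the comparisons of each SB623 group versus sham control". For the primary endpoint, section 9.1.1 adds: "A separate analysis will be repeated for the comparisons of each SB623 group versus sham control for FMMS response". Sections 9.1.2 and 9.2.1 to 9.2.5 follow the same pattern. No table or figure title in section 14 names a comparison between the doses.

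The SAP keeps other by-dose output. Summary tables are "displayed as 2.5 million SB623 cells, 5 million SB623 cells, Combined SB623 cells, and Sham Surgery for the efficacy analyses", section 9.1.1 plans a forest plot of individual and combined SB623 against sham, and section 9.3 plans LS-mean plots by dose. Section 12 lists analyses added to the protocol's set; nothing lists one as removed. Protocol 18.8 requires departures from the planned analysis to be explained in the final clinical report.

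**The concern.** A programmer who follows the SAP will not produce a randomised comparison that the protocol promises, and nothing shows whether this was a decision or an oversight. With no record, the contrast could be left out or brought back after unblinding, depending on the results.

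The planned output also invites an indirect reading. Each dose is set beside sham in the tables and forest plots, and section 9.3 puts p-values for each SB623 group against sham on the LS-mean plots. If one dose is significant against sham and the other is not, that does not show that the doses differ. The direct contrast answers that question, and it is the one left out.

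**Working it through.** **1. The plan's own sample size.** Inputs from protocol 18.7: 33% versus 11.7%, two-sided alpha 0.05, power 80%, allocation 2:1. The pooled rate is (0.117 + 2×0.33)/3 = 0.259. Sham n = [1.96×√(1.5×0.259×0.741) + 0.842×√(0.117×0.883 + 0.33×0.67/2)]² / 0.213² = 45.8, so 46 sham + 92 treated = 138, as stated. Allowing 10% dropout, 46/0.9 = 51.1, rounded up to 52 per arm; 3×52 = 156, as stated. The trial is sized for pooled versus sham. Neither document gives a sample size or power for dose against dose.

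**2. Precision of the dose contrast.** Assume 33% response at both doses and an unadjusted comparison. Half-width = 1.96×√(2×0.33×0.67/n).

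| n per dose | Basis | Half-width |
|---|---|---|
| 52 | all randomised | 18.1 points |
| 47 | 52×0.9 = 46.8 | 19.0 points |
| 46 | evaluable target, 92/2 | 19.2 points |

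On the odds-ratio scale, an observed OR of 1 has a 95% CI of about 0.44 to 2.26 with 52 per dose, and 0.42 to 2.38 with 46.

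**3. Power of the dose contrast.** Two-proportion test, with rates placed symmetrically around 33% (assumed).

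| True difference | 46 per dose | 52 per dose |
|---|---|---|
| 10 points | 17% | 19% |
| 20 points | 53% | 58% |
| Difference giving 80% power | about 27 points | about 26 points |

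**4. Why two comparisons with sham are not a substitute.** Both use the same sham arm, so their errors are correlated. With 46 per arm, the variance is 0.33×0.67/46 = 0.00481 for a dose arm and 0.117×0.883/46 = 0.00225 for sham, so each dose-versus-sham difference has variance 0.00705. Treating the two differences as independent gives a half-width of 1.96×√(2×0.00705) = 23.3 points. The sham term in fact cancels from the dose difference, which leaves 19.2 points.

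Reading significance side by side is worse. Suppose both doses truly have 33% response and sham 11.7%, with unadjusted two-sided z-tests. The exact binomial probability that exactly one dose reaches p<0.05 against sham is 28% with 46 per arm and 26% with 52. In those trials the direct dose test is non-significant about 86 to 87% of the time, so it would usually prevent the misreading.

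**5. Whether the SAP produces the contrast by another route.** The sample code in SAP Appendix I requests pairwise LS-mean differences. These include 5 million versus 2.5 million only if treatment has three levels in one model. Section 9.1.1 speaks of a separate analysis for each dose versus sham and does not say whether that is one three-level model or two two-group models. Under the second reading the contrast is never computed; under the first it is computed, but nothing requires it to be reported.

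**The case against.** The strongest reply is that much dose information survives and that the missing contrast is weak. Each dose has its own column, and an odds ratio or LS-mean difference against sham with a 95% CI. A reader could work out an unadjusted difference for the responder endpoints from the tabulated counts. Section 9.3 also summarises the primary endpoint within the SB623 arms by viable cells per mL. The contrast has 17 to 19% power for a 10-point difference, and the primary hypothesis, alpha and sample size do not depend on it. No SAP sentence cancels the protocol's requirement, and protocol 18.8 gives the clinical report the job of explaining departures.

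Most of this stands, and it rules out two stronger readings:

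- A reader might infer that the trial yields no dose comparison at all. The by-dose columns, estimates and plots show otherwise.
- A reader might infer that the trial loses its check on pooling the doses. Neither document gives the contrast that role, and section 4.1 of the protocol reports no apparent dose response in the Phase 1/2a study. The contrast would also be a weak check: an interval of about ±18 to 19 points cannot show similarity.

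The reply does not dispose of the gap itself. The protocol asks for the model-based comparison between doses, and by-dose displays are not that analysis. Low precision is a reason to report an interval and label it honestly. An explanation in the clinical report would meet 18.8, but it would come after the results are known.

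**Conclusion.** The gap is real and limited. Protocol 18.2.1.2 requires a direct dose comparison on the primary and all secondary efficacy endpoints; the SAP specifies only comparisons with sham and gives no reason. The documents support calling this an unrecorded omission. They do not show a deliberate removal, and they do not support saying that dose information is absent or that the pooled analysis is invalid.

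The cost is a missing estimate with a half-width of about 18 to 19 points on the primary endpoint, together with displays that would wrongly suggest a dose effect in about one trial in four if read by significance alone. These figures assume 33% response at each dose, 11.7% on sham, 46 to 52 subjects per arm and unadjusted comparisons; the planned covariate-adjusted models will differ somewhat. The SAP should be corrected, but the primary conclusion does not turn on it.

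**What to change.** In SAP 9.1.1 and 9.2.1 to 9.2.5:

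- State that the by-dose analysis fits one model with a three-level treatment factor (2.5 million, 5 million, sham).
- Report 5 million versus 2.5 million at Month 6, as an odds ratio for the responder endpoints and an LS-mean difference for NeuroQOL, with a 95% CI.
- Label the contrast descriptive and low-powered, and note that a null result does not show that the doses are similar.

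Extending this to the FMMS-change model in section 9.1.2 is optional, because SAP section 12 lists that analysis as an addition to the protocol's set. If the sponsor does not want the contrast, the SAP should record and justify its removal before unblinding, and the clinical report should repeat this under protocol 18.8.

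The cost is one contrast per model and one extra column per table. No new data are needed, and the primary analysis does not change.
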